### 2.2 SECONDARY OBJECTIVES

- To evaluate the safety of neoadjuvant dabrafenib and trametinib and adjuvant dabrafenib, trametinib and spartalizumab
- To determine the 12-month relapse free survival (RFS) rate in stage IIIB/C/D
- Melanoma patients who, after 8 weeks of neoadjuvant dabrafenib and trametinib, achieve a pCR and receive adjuvant dabrafenib and trametinib.
- To assess the recurrence patterns, distant metastasis-free survival (DMFS), and overall survival (OS) in all patients treated on protocol.

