### **Sample Size and Power**

A sample size argument will be based upon patients who do not have a pCR. We expect approximately 60% of enrolled patients to not achieve a pCR after 8 weeks on the dabrafenib/trametinib combination. Historically, these patients experience a 12-month relapse-free survival (RFS) rate of 50%, and we hope to increase this to 75%. Under the assumptions of 2 years for patient accrual and an additional 2 years of follow-up after accrual ends, exponentially- distributed RFS times, and a two-sided exponential maximum-likelihood test with a 5% Type 1 error rate (alpha), a total of 24 non-pCR patients will provide 80% power to detect a minimum increase in RFS at 1 year to 75%. If 60% of patients do not have a pCR, we would need to enroll a total of 40 patients to have a total of 24 non-pCR patients, but to account for a potentially higher pCR rate and patient dropout, we will accrue a total of 45 patients.

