### **Statistical Analyses**

For the primary objective, separately by group (patients who do/do not achieve a pCR at 8 weeks), the 12-month RFS rate will be estimated with a 95% confidence interval by using the Kaplan-Meier method. RFS is defined from time of surgery to any recurrence event (local or distant disease development or death due to melanoma. In addition, in patients who do not achieve a pCR, the 12-month RFS rate will be compared with the historical rate of 50% by using a two-sided exponential MLE test. Cox proportional hazards regression models will be fit to assess the association between various clinical, demographic, and disease covariates and RFS separately by pathologic response group.

For safety, the rate of grade 3+ adverse events will be tabulated and presented by group. For overall survival (OS) and distant metastasis-free survival (DMFS), 12-month rates will be reported with 95% confidence intervals, and Cox regression models will be used to assess the association between similar covariates as above and both OS and DMFS separately by group. OS is defined as time from treatment initiation to death. DMFS is defined as time from treatment initiation to development of documented distant metastatic disease outside the loco-regional site of the primary tumor or lymph node metastasis.

For the exploratory objectives, immunological and molecular features will be assessed quantitatively at baseline and at surgical resection. Kruskal-Wallis tests will be used to compare these parameters at each time point between responders (pCR) and non-responders (no pCR). Changes in each parameter from baseline to surgery will also be compared between responders and non-responders. Circulating tumor markers will be assessed at baseline and several on-study time points. Markers and changes in markers over time will be compared between responders and non-responders by using Kruskal-Wallis tests. In addition, generalized linear mixed models may be used to model these markers over time.

Finally, to assess the impact of neoadjuvant therapy on surgical resectability, a survey will be provided to surgeons regarding the difficulty of surgery (Appendix D). These data will be subjective and will be summarized graphically as numbers permit.

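### DMFS has no death term, so a patient who dies without documented distant metastasis is never a failure and reported DMFS can exceed OS

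*Combined protocol and SAP*

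**What the plan says.** DMFS is a secondary endpoint. Section 2.2 lists it beside OS ("To assess the recurrence patterns, distant metastasis-free survival (DMFS), and overall survival (OS) in all patients treated on protocol") without defining it. The Overview in Section 7.0 names it again, under recurrence patterns, also without a definition.

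The one definition is in Section 7.0, Statistical Analyses: "DMFS is defined as time from treatment initiation to development of documented distant metastatic disease outside the loco-regional site of the primary tumor". The sentence closes with a reference to nodal disease ("outside the loco-regional site of the primary tumor or lymph node metastasis"), which describes location and adds no death event on any reading.

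The neighbouring endpoints do include death. The sentence just before reads "OS is defined as time from treatment initiation to death", with the same starting point as DMFS. RFS counts "any recurrence event (local or distant disease development or death due to melanoma". For OS and DMFS the planned analysis is that "12-month rates will be reported with 95% confidence intervals, and Cox regression models will be used", by pathologic response group. Nothing says whether a death without documented distant metastasis is an event, a censoring or a competing event.

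**The concern.** The name says survival, but under the definition dying is not a failure. In an ordinary time-to-event analysis the patient who dies first leaves the risk set as censored. A Kaplan-Meier rate built that way treats the dead patient as having the same future metastasis risk as those still alive. It therefore overstates the proportion alive and free of distant metastasis. The Cox model becomes a model for the cause-specific hazard of metastasis, which can be interpreted but is not a model for DMFS.

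The setting makes the gap more than formal:

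- The event must be documented, and scheduled adjuvant disease assessments (Section 4.3, Tables 11 and 12) fall at weeks 20, 32 and 44 and at end of treatment, about 12 weeks apart.
- Brain relapse in non-pCR patients motivates the trial (Section 1.3), and a rapid decline could end in death before imaging.
- A toxic death would be an event in neither DMFS nor RFS, because RFS counts only melanoma deaths. Only OS would show it.
- Only the non-pCR group receives spartalizumab, so any upward bias from treatment-related deaths could differ between the two groups reported.

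A DMFS without deaths is also not comparable with any DMFS that counts them.

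**Working it through.** The plan states no DMFS or OS figure, so there is none to reproduce. The check asks what the definition does to a 12-month rate.

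**Inputs**

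- Event definitions and common time origin: Section 7.0, Statistical Analyses.
- Group sizes: 24 non-pCR patients and 45 in total (Section 7.0, Sample Size and Power: "we will accrue a total of 45 patients"). The 60% non-pCR rate given there yields 45 × 0.60 = 27 non-pCR and 45 − 27 = 18 pCR patients if all 45 reach surgery.
- Event counts: not in the documents, so assumed. Follow-up to month 12 is taken as complete.

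**Effect of one death without metastasis, no earlier metastasis**

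As written, the rate stays at 100%. With death counted it is 1 − 1/n. The difference is 1/n:

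- 1/24 = 4.2 points and 1/27 = 3.7 points (non-pCR)
- 1/18 = 5.6 points (pCR)
- 1/45 = 2.2 points (all patients)

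Two such deaths in the non-pCR group give at most 2/24 = 8.3 or 2/27 = 7.4 points.

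**With metastases as well**

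Let m be patients with distant metastasis, d deaths without it, and k deaths after it, all by month 12.

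- OS = 1 − (d + k)/n
- DMFS counting death = 1 − (m + d)/n
- DMFS as written = product of (1 − 1/r) over the metastases, where r is the number at risk and deaths are censored. This depends on the order of events, so it is averaged over random orders.

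Example, n = 24, m = 2, d = 2, k = 1:

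- Metastases first: 23/24 × 22/23 = 91.7%. Deaths first: 21/22 × 20/21 = 90.9%. Average over all orders: 91.3%.
- OS = 1 − 3/24 = 87.5%.
- DMFS counting death = 1 − 4/24 = 83.3%.

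The definition adds 91.3 − 83.3 = 8.0 points and puts DMFS above OS.

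| n | m / d / k | DMFS as written | OS | DMFS counting death |
|---|---|---|---|---|
| 24 | 0 / 1 / 0 | 100% | 95.8% | 95.8% |
| 24 | 1 / 1 / 1 | 95.7% | 91.7% | 91.7% |
| 24 | 2 / 2 / 1 | 91.3% | 87.5% | 83.3% |
| 24 | 2 / 3 / 1 | 91.1% | 83.3% | 79.2% |
| 24 | 4 / 3 / 2 | 82.1% | 79.2% | 70.8% |
| 24 | 4 / 2 / 2 | 82.5% | 83.3% | 75.0% |
| 24 | 6 / 1 / 1 | 74.4% | 91.7% | 70.8% |
| 45 | 2 / 2 / 1 | 95.5% | 93.3% | 91.1% |

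DMFS as written exceeds OS roughly when d is greater than m − k, that is, when deaths without metastasis outnumber patients alive with it. The 4/2/2 and 6/1/1 rows show that this need not happen. With death counted, DMFS is at or below OS in every row, as it must be when both run from the same origin.

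**The case against.** Five points can be made for the plan.

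- **Censoring at death is inferred.** Kaplan-Meier is named only for RFS. This stands as a matter of text. Censoring is nevertheless what the definition produces in a time-to-event rate and a Cox model, and the absence of a stated rule is a gap in itself.
- **The endpoint may be meant as time to metastasis.** The Overview groups it with recurrence patterns, which fits that reading. The faults are then the label and the missing competing-risk treatment. The endpoint still needs correcting, by the second route given under the fix.
- **Surveillance is regular.** Scheduled body and brain imaging makes undocumented distant disease within 12 months less likely, and extra scans are allowed. This lowers the expected number of such deaths. It does nothing for toxic or other non-melanoma deaths.
- **The magnitude is assumed.** True. The 8-point figure puts two deaths in the non-pCR group, and 1/n is the upper case. With six metastases and one such death in 24 patients the gap is 74.4 − 70.8 = 3.6 points rather than 4.2.
- **The consequence is limited.** DMFS is secondary, has no benchmark test, and is reported beside OS. At an assumed 90% rate and n = 24, the 95% half-width is 1.96 × √(0.9 × 0.1/24) = 0.12, or 12 points, which is wider than the shift. That limits the importance of the point, but imprecision does not excuse a systematic upward error.

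**Conclusion.** The concern holds. The only DMFS definition omits death altogether. The reported rate would therefore be biased upward as a survival measure, and it can exceed OS, although it will not always do so.

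For 0 to 2 deaths without documented metastasis by month 12, the shift is 0 to about 8 points in 24 to 27 non-pCR patients. It is up to 2.2 points per death across all 45. These figures rest on an assumed number of deaths, complete 12-month follow-up and, for the 27 and 18 group sizes, a 60/40 split with every patient reaching surgery. If no such death occurs, the effect is zero.

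The primary RFS analysis and the sample size do not depend on this. It should be corrected before the data are analysed, so that the choice is not made with the deaths in view.

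**What to change.** In Section 7.0, Statistical Analyses, define DMFS as the time from the start of treatment to the first documented distant metastasis or death from any cause, whichever comes first. State how patients alive without distant metastasis are censored.

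If time to distant metastasis is also wanted, give it that name. Report it as a cumulative incidence with death without metastasis as a competing event, and label any Cox model that censors at death as cause-specific.

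The cost is a sentence or two. Deaths are already collected for OS, so no new data or patients are needed. The reported DMFS rate may come out slightly lower.

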## **8.0 INSTITUTIONAL REVIEW BOARD (IRB) APPROVAL**

The investigator (i.e., the study site principal investigator) will obtain, from the MD Anderson Cancer Center Institutional Review Board (IRB), prospective approval of the clinical protocol and corresponding informed consent form(s); modifications to the clinical protocol and corresponding informed consent forms, and advertisements (i.e., directed at potential research subjects) for study recruitment, if applicable.

The only circumstance in which a deviation from the current IRB-approved clinical protocol/consent form(s) may be initiated in the absence of prospective IRB approval is to eliminate an apparent immediate hazard to the research subject(s). In such circumstances, the investigator will promptly notify the MD Anderson Cancer Center IRB of the deviation.

The MD Anderson Cancer Center IRB operates in compliance with FDA regulations at 21 CFR Parts 50 and 21 CFR 56, and in conformance with applicable International Conference on Harmonization (ICH) Guidelines on Good Clinical Practice.

## **9.0 COMPLIANCE WITH TRIAL REGISTRATION AND RESULTS POSTING REQUIREMENTS**

Under the terms of the Food and Drug Administration Modernization Act (FDAMA) and the Food and Drug Administration Amendments Act (FDAAA), the Sponsor of the trial is solely responsible for determining whether the trial and its results are subject to the requirements for submission to the Clinical Trials Data Bank, <http://www.clinicaltrials.gov>. Information posted will allow subjects to identify potentially appropriate trials for their disease conditions and pursue participation by calling a central contact number for further information on appropriate trial locations and trial site contact information.

## **10.0 ETHICAL CONSIDERATIONS**

The clinical study will be conducted in accordance with the current IRB- approved

clinical protocol; ICH Guidelines on Guidelines on Good Clinical Practice; and relevant policies, requirements, and regulations of the University of Texas MD Anderson Cancer Center IRB, and applicable federal agencies.

## **11.0 INFORMED CONSENT**

The investigator (i.e., the study site principal investigator) will make certain that an appropriate informed consent process is in place to ensure that potential research subjects, or their authorized representatives, are fully informed about the nature and objectives of the clinical study, the potential risks and benefits of study participation, and their rights as research subjects. The investigator, or a sub-investigator(s) designated by the MD Anderson IND Office, will obtain the written, signed informed consent of each subject, or the subject's authorized representative, prior to performing any study-specific procedures on the subject. The date and time that the subject, or the subject's authorized representative, signs the informed consent form and a narrative of the issues discussed during the informed consent process will be documented in the subject's case history. The investigator or sub-investigator will retain the original copy of the signed informed consent form, and a copy will be provided to the subject, or to the subject's authorized representative.

## **12.0 STUDY DOCUMENTATION, MONITORING, AND ADMINISTRATION**

The investigator and the head of the medical institution (where applicable) agrees to allow the IND Office monitor direct access to all relevant documents and to allocate their time and the time to their staff to monitor to discuss findings and any issues.

- Monitoring visits will be conducted in a manner to ensure that the:
- Data are authentic, accurate, and complete.
- Safety and rights of subjects are being protected.
- Study is conducted in accordance with the currently approved protocol and any other study agreements, ICH GCP, and all applicable regulatory requirements.

## APPENDICES

### Appendix A: Eastern Cooperative Oncology Group (ECOG) Performance Status Scale

Grade	Description
0	Fully active, able to carry on all pre-disease performance without restriction
1	Restricted in physically strenuous activity but ambulatory and able to carry out work of a light or sedentary nature, e.g., light housework or office work
2	Ambulatory and capable of all self-care but unable to carry out any work activities; up and about > 50% of waking hours
3	Capable of only limited self-care, confined to a bed or chair > 50% of waking hours
4	Completely disabled; cannot carry on any self-care; totally confined to bed or chair
5	Dead

## Appendix B: Management of Spartalizumab-Induced Immune Mediated AEs

## Recommended clinical management for suspected immune-related diarrhea/colitis

Diarrhea/colitis (NCI-CTCAE v5)	
Grade	Recommended management
Grade 1 (Increase of < 4 stools per day over baseline) mild increase in ostomy output compared to baseline.	
 
Diet & Hydration
 
Loperamide: initially 4 mg, followed by 2 mg every four hours or after every unformed stool; maximum 16 mg/d. Continue until free of diarrhea for 12h
 
Diarrhea > 24h: loperamide 2 mg every two hours; maximum 16 mg/d. Consider adding oral antibiotics.
 
Diarrhea > 48h: loperamide 2 mg every two hours; maximum 16 mg/d. Consider other second-line therapies for diarrhea (e.g. octreotide, oral diphenoxylate) and oral antibiotics
 
If grade 2 and no improvement in 5 days: consider oral steroids
 
If grade 2 diarrhea persists > 1 week consider gastroenterologist consultation and endoscopy to evaluate for colitis
 
If grade 2 persists for 5 days and worsening of symptoms or diffuse ulcerations and bleeding seen on endoscopy, initiate steroids (0.5 - 1 mg/kg/d of prednisone or equivalent) and continue until symptoms improve to grade 1.
 
If no improvement occurs, manage as per grade 3. Steroids should be tapered slowly
 
Sigmoidoscopy and biopsy can be considered and may assist in determining the duration of steroid taper based on the evidence of macroscopic and microscopic inflammation.
 

Grade 3 diarrhea: Increase of $\geq$ 7 stools per day over baseline; incontinence; hospitalization indicated; severe increase in ostomy output compared to baseline; limiting self-care ADL;  Grade 3 colitis: Severe abdominal pain; change in bowel habits; medical intervention indicated; peritoneal signs	
 
Clinical evaluation and hospitalization indicated; rule out bowel perforation and intravenous hydration.
 
Consider consultation with gastroenterologist and biopsy with endoscopy.
 
In addition to symptomatic treatment (diet, hydration, loperamide, antibiotics if indicated); initiate immediate treatment with intravenous steroids (methylprednisolone 125 mg) followed by high dose oral steroids (prednisone 1 to 2 mg/kg once per day or dexamethasone 4 mg every 4 hours) is recommended.
 
When symptoms improve to <math>\leq</math> grade 1, taper steroids slowly (see Taper over 6 to 8 weeks in patients with diffuse and severe ulceration and/or bleeding).
 
If no improvement in 2-3 d: consider initiating infliximab 5 mg/kg and continue steroids. Note: infliximab is contraindicated in patients with sepsis or a perforation. Upon symptomatic relief initiate a prolonged steroid taper over 6 to 8 weeks.
 
If symptoms worsen during steroid reduction, initiate a re-tapering of steroids starting at a higher dose of 80 or 100 mg/d followed by a more prolonged taper and administer infliximab.
 
If symptoms persist despite the above treatment a surgical consult should be obtained.
 

Grade 4: Life-threatening consequences; urgent intervention indicated	Same as grade 3
---	-----------------

Recommended clinical management for suspected immune-related liver laboratory alterations

Abnormal liver tests (NCI-CTCAE v5)	
Grade	Recommended management
Grade 2:  AST or ALT $> 3 \times \text{ULN}$ to $\leq 5.0 \times \text{ULN}$ ; or if baseline abnormal $> 3.0 - 5.0 \times \text{baseline}$  or bilirubin $> 1.5 \times \text{ULN}$ to $\leq 3 \times \text{ULN}$ ; or if baseline abnormal $> 1.5 - 3.0 \times \text{baseline}$  (if patient meets criteria for Hy's law refer to	
 
Monitor hepatic laboratory tests more frequently (every 2-3 days) until returned to baseline values
 
Rule-out alternative causes (e.g. concomitant medications, infection, disease progression)
 
Consider prednisone (0.5-1 mg/kg/d) if liver tests worsen and/or significant symptoms
 

Grade 3 or 4: AST or ALT $> 5.0 \times \text{ULN}$ ; or if baseline abnormal $> 5.0 \times \text{baseline}$ .  bilirubin $> 3.0 \times \text{ULN}$ ; or if baseline abnormal $> 3.0 \times \text{baseline}$ .	
 
Monitor hepatic laboratory tests more frequently (every 2-3 days) until returned to baseline values.
 
Consider viral serology (i.e. hepatitis A/B/C, CMV, and rule out other potential cause of liver injury such as concomitant medications or alcohol), consultation with hepatologist and liver biopsy to establish etiology of hepatic injury
 
If after 2-3 days new liver assessment shows worsening of laboratory test consider to initiate treatment with steroids prednisone 1-2 mg/kg/day or i.v. equivalents.
 
Add prophylactic antibiotics for opportunistic infections as appropriate
 
When symptoms/liver tests improve to grade <math>\leq 1</math>, taper steroids over at least 4 weeks.
 
If serum transaminase levels or bilirubin do not decrease 48-72 hours after initiation of systemic steroids, oral mycophenolate mofetil 500 mg every 12 hours may be given as per institutional guidelines.
 
Infliximab is not recommended due to its potential for hepatotoxicity
 

Recommended clinical management for suspected immune-related rash and other skin events

Rash and other skin Events (NCI-CTCAE v5)	
Grade	Recommended management
Grade 1: rash covering < 10% Body Surface Area (BSA)	
 
Initiate prophylactic and symptomatic treatment measures.
 
Consider use of topical corticosteroids or urea containing creams in combination with oral antipruritics or moderate strength topical steroid (hydrocortisone 2.5% cream or fluticasone propionate 0.5% cream)
 
Reassess after 2 weeks.
 

Rash and other skin Events (NCI-CTCAE v5)	
Grade	Recommended management
Grade 2: 10-30% of BSA	
 
If tolerable, treat as per grade 1;
 
If intolerable, initiate systemic steroids (e.g. oral prednisolone 0.5- 1 mg/kg/d) and consider dose interruption until tolerable or recovery to grade <math>\leq</math> 1 or baseline
 
If symptoms persist or recur consider skin biopsy.
 

Grade 3: More than 30% of BSA	
 
Obtain a skin biopsy and dermatology consult.
 
Initiate systemic steroids with 1mg/kg/d of prednisone or equivalent.
 

Grade 4: Life-threatening	Same as grade 3; additional measures as per local institutional guidelines
Other skin events	
Stevens-Johnson syndrome, toxic epidermal necrolysis	
 
Hospitalization and urgent dermatology consultation
 
Institute supportive care immediately as per institutional guidelines
 

Recommended clinical management for suspected immune-related nephritis

Nephritis (NCI-CTCAE v5)	
Grade	Recommended management
Grade 1: Creatinine $>$ ULN to $\leq$ 1.5 $\times$ ULN; or if baseline abnormal $>$ 1 – 1.5 x baseline	
 
Monitor creatinine weekly
 
If creatinine return to baseline resume routine creatinine monitoring per protocol
 
Promote hydration and cessation of nephrotoxic drugs
 

Grade 2: Creatinine $>$ 1.5 to $\leq$ 3 $\times$ ULN; or if baseline abnormal $>$ 1.5 – 3.0 x baseline	
 
Monitor creatinine every 2 to 3 days
 
Initiate 0.5 to 1 mg/kg/d prednisone or equivalents
 
If worsening or no improvement: 1 to 2 mg/kg/day prednisone or equivalents
 
Promote hydration and cessation of nephrotoxic drugs
 
Consult with specialist and consider renal biopsy
 

Grade 3: Creatinine $>3.0$ to $\leq 6.0 \times$ ULN; or if baseline abnormal $>3.0 - 6.0 \times$ baseline	
 
Monitor creatinine every 1 to 2 days
 
Start 1 to 2 mg/kg/day prednisone or equivalents
 
Consult with nephrologist and consider renal biopsy
 

Grade 4: Creatinine $> 6.0 \times$ ULN	
 
Monitor creatinine daily
 
Initiate steroids with 1 to 2 mg/kg/d prednisone or equivalent
 
Consult with nephrologist and consider renal biopsy
 

Recommended clinical management for suspected immune-related pneumonitis

Pneumonitis (NCI-CTCAE v5)	
Grade	Recommended management
Grade 1: Asymptomatic; clinical or diagnostic observations only; intervention not indicated	
 
High-resolution CT with lung windows recommended, with serial imaging to monitor for resolution or progression. Repeat at least every 3 weeks
 
Monitor for symptoms every 2-3 days - Clinical evaluation and laboratory work-up for infection
 
Monitoring of oxygenation via pulse oximetry recommended
 

Pneumonitis (NCI-CTCAE v5)	
Grade	Recommended management
	
 
Consultation of pulmonologist recommended
 

Grade 2: Symptomatic-medical intervention indicated; limits instrumental ADLs	
 
Perform high-resolution CT with lung windows
 
Monitor symptoms daily, consider hospitalization
 
Clinical evaluation and laboratory work up for infection
 
Consult pulmonologist
 
Pulmonary function tests - if normal at baseline, repeat every 8 weeks
 
Bronchoscopy with biopsy and/or BAL recommended
 
Symptomatic therapy including corticosteroids if clinically indicated (1 to 2 mg/kg/d prednisone or equivalent as clinically indicated).
 

Grade 3: Severe symptoms; limits self-care ADLs; oxygen indicated	
 
Hospitalization and pulmonary and infectious disease consultation
 
Methylprednisolone (1-2 mg/kg/d or equivalent) until symptoms improve to Grade <math>\leq 1</math>, then slow taper over <math>\geq 4-6</math> weeks
 

Grade 4: Life- threatening respiratory compromise; urgent intervention required	
 
If no improvement within 48 hours, consider infliximab and/or other immune-suppressive therapy, or i.v. Ig as per local guidelines
 
Empiric antibiotics
 

Recommended clinical management for suspected immune-related endocrinopathies

Endocrine events (NCI-CTCAE v5)	
Grade	Recommended management

Asymptomatic, intervention not indicated (e.g. hyperthyroidism or hypothyroidism)	
 
• If <math>TSH < 0.5 \times LLN</math>, or <math>TSH > 2 \times ULN</math>, or consistently out of range in 2 subsequent measurements, include free T4 at subsequent cycles as clinically indicated
 
• Consider endocrinologist consult
 
• If hypophysitis is considered, pituitary gland imaging should be considered (MRIs with gadolinium and selective cuts of the pituitary can show enlargement or heterogeneity and confirm the diagnosis)
 
• Repeat labs in 1 to 3 weeks/MRI in 1 month if laboratory abnormalities persist but normal lab/pituitary scan
 

Symptomatic endocrinopathy (e.g., hypophysitis, adrenal insufficiency, hypothyroidism, hyperthyroidism)	
 
• Endocrinology consultation
 
• Rule out infection/sepsis and other alternative causes with appropriate cultures and imaging
 
• Evaluate hormone levels (e.g. ACTH, cortisol, FSH/LH, TSH, free T4, testosterone/estrogen), metabolic panel (e.g. Na, K, CO2, glucose), and imaging (e.g. brain MRI) as clinically indicated
 
• Initiate hormone replacement therapy as appropriate
 
• Consider steroids (methylprednisolone 1 to 2 mg/kg/d or equivalent) in case of severe hypophysitis or thyrotoxicosis
 
• Replacement of appropriate hormones may be required as the steroid dose is tapered
 
• Hypophysitis with clinically significant adrenal insufficiency and hypotension, dehydration, and electrolyte abnormalities (such as hyponatremia and hyperkalemia) constitutes adrenal crisis
 
• Consider a beta-blocker in case of severe hyperthyroidism.
 

Endocrine events (NCI-CTCAE v5)	
Grade	Recommended management
	
 
• Consider hospitalization (e.g. in case of severe adrenal insufficiency/crisis), fluid replacement, and other supportive measures as clinically be initiate
 

Autoimmune diabetes (Grade 3 or symptomatic hyperglycemia)	
 
• Initiate anti-glycemic therapy (i.e. insulin) as medically indicated and monitor glucose levels regularly until metabolic control is achieved
 
• Evaluate for ketoacidosis as medically indicated
 
• Consultation with endocrinologist
 
• Consider hospitalization (e.g. in case of ketoacidosis)
 

Autoimmune diabetes (Grade 4 hyperglycemia or life-threatening complications)	Same as grade 3

Recommended clinical management for suspected infusion reaction or cytokine release syndrome

Infusion reaction (NCI-CTCAE v5)	
Grade	Recommended management
Grade 1 Mild reaction; infusion interruption not indicated; intervention not indicated	
 
• Increase monitoring of vital signs as medically indicated until the patient is deemed medically stable in the opinion of the investigator.
 
• Consider slowing infusion rate until recovery of symptoms
 
• May continue spartalizumab
 

Grade 2 Requires infusion interruption but responds promptly to symptomatic treatment (e.g., antihistamines, NSAIDS, narcotics, IV fluids); prophylactic medications indicated for <=24 hrs	
 
• Stop infusion
 
• Additional medical therapy as per local institutional guidelines that may include: 
 
• i.v. fluids
 
• Antihistamines
 
• NSAIDS
 
• Acetaminophen
 
• Narcotics
 
• Oxygen and corticosteroids as indicated
 
 
 
• Increase monitoring of vital signs as medically indicated until the patient is deemed medically stable in the opinion of the investigator.
 
• If symptoms resolve within one hour of stopping drug infusion, the infusion may be restarted at 50% of the original infusion rate (e.g. from 100 mL/hr to 50 mL/hr). Otherwise dosing will be held until symptoms resolve and the patient should be re-premedicated for the next scheduled dose.
 
• Patient may be premedicated 1.5h (<math>\pm</math> 30 minutes) prior to infusion with diphenhydramine 50 mg p.o. (or equivalent dose of antihistamine) and acetaminophen 500-1000 mg p.o. (or equivalent dose of analgesic).
 
• Consider permanent discontinuation of study treatment in case of recurring infusion reaction despite premedication and prolonged infusion
 

Grade 3:	
 
• Stop infusion
 

Infusion reaction (NCI-CTCAE v5)	
Grade	Recommended management

Prolonged (i.e., not rapidly responsive to symptomatic medication and/or brief interruption of infusion); recurrence of symptoms following initial improvement; hospitalization indicated for other clinical sequelae (e.g., renal impairment, pulmonary infiltrates)
 
Grade 4:
 
Life-threatening; pressor or ventilatory support indicated
	
 
• Additional medical therapy as per local institutional guidelines that may include: 
 
• i.v. fluids
 
• Antihistamines
 
• NSAIDS
 
• Acetaminophen
 
• Narcotics
 
• Oxygen
 
• Corticosteroids
 
• Epinephrine
 
 
 
• Close monitoring of vital signs, pulse oximetry and ECG as medically indicated until the subject is deemed medically stable.
 
• Hospitalization as indicated
 

--	---

Recommended clinical management guidelines for suspected other potential immune-related events

[figure not shown]

Other (i.e. Autoimmune neuropathy, Demyelinating polyneuropathy, Guillain Barre, Myasthenia Gravis-like syndrome, non-infectious myocarditis, pericarditis, pancreatitis, encephalitis, and Grade 3 Fatigue with rapid onset in absence of disease progression) (NCI-CTCAE v5)
	
Grade	Recommended management
Mild (Grade 1)	Provide symptomatic treatment
Moderate (Grade 2)	
 
• Consider treatment interruption until recovery to <math>\leq</math> grade 1 or baseline.
 
• Ensure adequate evaluation to confirm etiology or exclude other causes
 
• Provide symptomatic treatment
 
• Systemic corticosteroids may be indicated
 
• Consider biopsy for confirmation of diagnosis
 
• A specialist should be consulted
 

Severe (Grade 3)	
 
• Initiate systemic corticosteroids (prednisone or equivalent) at a dose of 1-2 mg/kg/d and other therapies as appropriate
 
• Monitor closely and consult with a specialist
 

Grade 4	
 
• Hospitalization and consult with specialist
 
• Initiate systemic corticosteroids (prednisone a dose of 1-2 mg/kg/d or equivalent) and other therapies as appropriate
 

Encephalitis (any grade) or aseptic meningitis	
 
• Rule out infectious or other causes of moderate to severe neurologic deterioration, and consult with specialist.
 
• If other etiologies are ruled out, administer corticosteroids at a dose of 1 to 2 mg/kg/d prednisone equivalents.
 

Guillain-Barre Severe peripheral or autonomic neuropathy, or transverse myelitis	
 
• Hospitalization and consult with specialist
 

Myasthenia gravis	
 
• Consult with specialist
 
• Consider pyridostigmine and systemic corticosteroids (prednisone or equivalent) at a dose of 1-2 mg/kg/d; other therapies as appropriate (e.g. IVIG)
 
• Hospitalization in case of severe cases
 

Other (i.e. Autoimmune neuropathy, Demyelinating polyneuropathy, Guillain Barre, Myasthenia Gravis-like syndrome, non-infectious myocarditis, pericarditis, pancreatitis, encephalitis, and Grade 3 Fatigue with rapid onset in absence of disease progression) (NCI-CTCAE v5)	
Grade	Recommended management
Myocarditis (any grade) or cardiac event grade $\geq 3$	Urgent cardiology consult is essential to initiate high dose systemic corticosteroids (prednisone or equivalent). Hospitalization as indicated
Pancreatitis Amylase/lipase elevation	
 
• Evaluate for pancreatitis (clinical assessment, abdominal imaging and/or magnetic resonance cholangiopancreatography as appropriate)
 
• Treatment may be continued in case of asymptomatic, isolated enzyme elevations without evidence for pancreatitis
 
• Initiate steroids in case of <math>\geq</math> grade 2 acute pancreatitis
 

Autoimmune hemolytic anemia, hemolytic uremic syndrome, or acquired hemophilia grade $\geq 3$	
 
• Consult with specialist
 
• Consider systemic corticosteroids and other therapies as appropriate (e.g. transfusion) per local institutional guidelines
 

